12.6.2 Radiation Dosimetry

Descriptive statistics of absorbed doses to the target organs and tissues specified in the MIRD schema will be tabulated. In addition, the absorbed doses to these target organs and tissues will be compared between the Chinese subjects from this study and European subjects by using the 2-sample t-test.

12.6.3 Effective Dose

ED will be calculated according to ICRP methodology of ICRP publication 60 [[ICRP 1991](#)]. In addition, the ED will be compared between the Chinese subjects from this study and European subjects by using the 2-sample t-test.

12.6.4 Statistical Hypothesis, Model, and Method of Analysis

No confirmatory hypothesis testing is intended to be performed in this study.

12.6.5 Handling of Missing Values/Censoring/Discontinuations

Missing values will not be substituted by estimated values but treated as missing in the statistical evaluation. All data from all subjects dosed in the study will be included in all listings, plots, summary tables, and statistical analyses when appropriate.

12.6.6 Supportive Analyses

No sensitivity analyses are currently planned in this study.

12.6.7 Handling of Uninterpretable Images

The number of images that are uninterpretable will be displayed in tables.

12.7 Interim Analysis

No interim analysis will be performed in this study.

12.8 Sample Size Calculation

No sample size calculations were performed. The number of subjects in this study was determined to fulfil local regulatory requirements.

12.9 Power for Analysis of Critical Secondary Variables

No power calculations were made on any secondary variables.

12.10 Procedures for Missing, Unused and Spurious Data

Missing values will not be substituted by estimated values but treated as missing in the statistical evaluation. All data from all subjects dosed in the study will be included in all listings, plots, summary tables, and statistical analyses when appropriate.

12.11 Rules for Excluding Subjects from Analysis

All dosed subjects with a complete set of images will be included in the analyses unless otherwise specified. The sponsor will make any decisions regarding whether any subjects or any individual values belonging to a subject will be excluded from the evaluations when the protocol violation is considered to have a negative impact on the scientific aspects and interpretation of the study results. Such judgments should be made in a blinded fashion before database lock and before any analyses have been performed. If the subject has received any IMP, all available safety data will be used. The reason(s) for any exclusion will be described in the report.

12.12 Procedures for Reporting Deviations from Original Statistical Plan

Any deviations from the statistical analysis outlined in this protocol will be described, and reasons for the deviations listed, in the final Clinical Study Report.

13 SPECIAL REQUIREMENTS AND PROCEDURES

13.1 Regulatory, Institutional and Ethical Review

Before starting this study, the protocol (authorised by the sponsor) will be submitted to the regulatory bodies/local health authorities (in accordance with local regulations) and to the IEC/IRB for evaluation. The protocol will also be signed by the principal investigator before submission to the IEC/IRB. The study will not start before the IEC/IRB gives written approval or a favourable opinion in accordance with ICH E6-GCP and all applicable regulatory bodies/local health authorities give approval or a favourable opinion as required.

No changes from the final approved (authorised) protocol will be initiated without the IEC's/IRB's prior written approval or favourable opinion of a written amendment, except when necessary to eliminate immediate hazards to the subjects or when the change involves only logistics or administration. The sponsor will authorise and the principal investigator(s) will sign the protocol amendment prior to submission to the IEC/IRB. Protocol amendments should be submitted to the IEC/IRB without delay. Any significant deviation from the protocol when no approved amendment exists will be regarded as a protocol violation and will be addressed as such during the reporting of the study.

13.2 Investigator's Responsibilities

13.2.1 Overall Responsibilities

The investigator(s) is/are responsible for conducting the study in full accordance with the Protocol and the Declaration of Helsinki, the *Good Clinical Practice: Consolidated Guideline*, approved by the ICH, and any applicable national and local laws and regulations. Information regarding any investigational centres participating in this study that cannot comply with these standards will be documented.

13.2.2 Subject Informed Consent

Written and oral information about the study in a language understandable by the subject will be given to all subjects. Each subject's willingness to participate in the study will be documented in a signed and dated informed consent form before any procedures or assessments are done and after the aims, methods, anticipated benefits, potential hazards, and insurance arrangements in force are explained. It will also be explained to the subjects that they are free to refuse entry into the study and free to withdraw from the study at any time without prejudice to future treatment. The informed consent process will be documented in the subject's medical record and the investigator will sign, date, and time the informed consent form after the subject has signed, dated, and recorded the time. The investigator(s) will keep the original consent forms, and copies will be given to the subjects.

13.2.3 Direct Access to Source Data/Documents

The monitor(s), auditor(s), authorised personnel of the sponsor/CRO, health authority inspector(s) or their agents, and authorised members of IECs/IRBs will be given direct access to source data and documentation (e.g., medical charts/records, laboratory results, printouts, videotapes, etc.) for source data verification, provided that subject confidentiality is maintained in accordance with local requirements.

13.2.4 Confidentiality Regarding Study Subjects

The investigator(s) must assure that the privacy of the subjects, including their personal identity and all other personal medical information, will be maintained at all times. In CRFs and other documents or image material (including materials from all examinations) submitted to the sponsor/CRO, subjects will not be identified by their names, but by an identification code (e.g., study subject number).

Personal medical information may be scrutinised for the purpose of verifying data recorded in the CRF. This may be done by the monitor(s), properly authorised persons on behalf of the sponsor, the quality assurance unit, or regulatory authorities. Personal medical information will always be treated as confidential.

13.3 Protocol Deviations

Any deviation from the protocol when no approved amendment exists must be documented as a protocol deviation and reported according to local requirements. If appropriate, corrective and preventative action must be implemented to avoid repetition. Protocol deviations and any potential impact on the study results will be discussed during the reporting of the study.

Waivers or protocol exceptions will not be granted prospectively by the sponsor under any circumstances.

13.4 Study Monitoring

Study monitoring will be performed in accordance with ICH E6-GCP, the sponsor/CRO SOPs, the protocol, and applicable local regulations.

13.5 Audit and Inspection

According to ICH E6-GCP, the sponsor or regulatory authorities may audit the investigational site. The sponsor's Quality Assurance Unit, independent of the Clinical Research and Development Department, is responsible for auditing the study.

The investigator(s) must accept that regulatory authorities may conduct an inspection to verify compliance of the study with GCP.

13.6 Insurance

This study is covered under the sponsor's Liability Insurance Policy (under General Electric Insurance Company and/or a company designated by the study sponsor). A Certificate of Insurance and/or an information leaflet containing essential information about the insurance coverage can be provided upon request.

13.7 Publication Policy

The investigator and/or Institution shall have the right to publish the results of their work conducted under this protocol, subject to providing the sponsor with the opportunity to review the contents of any proposed abstract or publication concerning the work, including any results of the study, in advance of publication and if necessary to delay publication for a limited time not to exceed 60 days in order to protect the confidentiality or proprietary nature of any information contained therein. The sponsor will make every reasonable effort to consider and release each proposed publication within 30 days, or proposed abstract within 15 days, of submission.

15 APPENDICES

15.1 Information on Investigational and Registered Products

The reference document for this study is the current version of the European Union Summary of Product Characteristics approved by the European Medicines Agency. The reference document provides up-to-date information on the efficacy and safety of the IMP and is used for assessing expectedness of Serious Adverse Drug Reactions, in order to determine regulatory reportability. An unexpected adverse drug reaction is a reaction for which the nature, seriousness, severity, or outcome is not consistent with the applicable product information.

15.2 Equipment Parameters

Please refer to the **Imaging Manual**.

15.3 Normal Limits for Vital Signs, Oxygen Saturation and ECG Intervals

Table 3 Criteria for Normal Limits for Vital Signs and Oxygen Saturation

| Vital Signs Parameter | Normal Limits | |
|-----------------------------------|----------------------|------------------|
| | Low | High |
| Systolic BP (mm Hg) | 85 | 139 |
| Diastolic BP (mm Hg) | 60 | 89 |
| Heart rate (beats/minute) | 60 | 100 |
| Respiration rate (breaths/minute) | 12 | 22 |
| Body Temperature | 36.4°C 97.5°F | 37.7°C 99.5°F |
| Oxygen saturation (%) | 93 | 100 |

^a Changes in body weight are evaluated by the investigator (without taking height into account) since BMI is not collected on the CRF.

^b BMI is calculated and analysed retrospectively by the sponsor, at which time height is taken into account.

Table 4 Criteria for Normal Limits for ECGs

| ECG Variable | Normal Limits (ms) | |
|--|--------------------|------|
| | Low | High |
| PR interval | 120 | 200 |
| QRS interval | 50 | 100 |
| RR interval | 600 | 1000 |
| QT interval (Sex not specified) | — | ≤440 |
| QTc interval ^a (Sex not specified) | — | ≤440 |

^a No lower boundary set for QTc.

15.4 Tolerability Questionnaire

Before and after the administration of DaTSCAN™ Injection, please ask the subject to mark on the line below how he/she is feeling with a single line (not a cross), to record the status of mood, pain at injection site, itchiness of injection site, loss of function at injection site, and quality of sleep, using Visual Analog Scale (VAS) method*.

Mood:

Pain at Injection Site:

Itchiness of Injection Site:

Loss of Function at Injection Site

Quality of Sleep[#]:

*Visual Analog Scale (VAS) is a continuous scale comprised of a horizontal line, usually 10 centimetres (100 mm) in length, anchored by 2 verbal descriptors: “0” stands for normal, and 100 mm stands for each symptom extreme, or “0” stands for bad, and 100 mm stands for good.

[#] At -1h (± 10 min), assessment is based on how subject feels during past 2 weeks' sleep quality; At 15mins (± 5 min), 1h (± 10 min), 4h (± 10 min), assessments seem to be not applicable; At 24h (± 2 h), assessment is based on quality of first sleep after IMP injection; At 48h (± 3 h), assessment is based on quality of second sleep after IMP injection.

Tolerability Questionnaire Scoring Table

| | Tolerability Questionnaire Timepoint ^{&} | | | | | |
|---|---|-------------------------|-----------------------|-----------------------|---------------------|---------------------|
| | -1h (± 10 min) | 15min (± 5 min) | 1h (± 10 min) | 4h (± 10 min) | 24h (± 2 h) | 48h (± 3 h) |
| Mood | | | | | | |
| Pain at Injection Site | | | | | | |
| Itchiness of Injection Site | | | | | | |
| Loss of Function at Injection Site | | | | | | |
| Quality of Sleep | | | | | | |

h = hours, min = minutes

[&]15mins, 1h, 4h, 24h, 48h mean various timepoints post administration of IMP. -1h means 1 hour before the administration of IMP.

Scoring Implication

| | | |
|------------------------------------|--------------|--------------------------|
| Mood | Bad – 0mm | Good – 100mm |
| Pain at Injection Site | Normal – 0mm | Painful – 100mm |
| Itchiness of Injection Site | Normal – 0mm | Itchy – 100mm |
| Loss of Function at Injection Site | Normal – 0mm | Loss of Function – 100mm |
| Quality of Sleep | Bad – 0mm | Good – 100mm |

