9.2.1 Before IMP Administration

During the baseline period (defined as “after the screening visit up to 1 hour prior to administration”), the following will be recorded/conducted:

- Confirm inclusion/exclusion criteria
- Concomitant medications recording
- Physical examination and injection site monitoring
- Vital signs and oxygen saturation
- Thyroid blocking (see Section 8.1.5)
- Urine β -hCG test for pregnancy (for women of child-bearing potential)
- AE monitoring

Subjects will avoid all food and drink (except water) for 2 hours before and 2.5 hours after injection of DaTSCAN™. Then, light meals and unlimited decaffeinated/noncarbonated drinks are permitted out to 6 hours after injection. After that, there are no food restrictions, but caffeinated/carbonated drinks are limited to 4 cups per 24-hour period.

For subject comfort and prior to IMP administration, subjects will be advised to empty their bladder, and if necessary, have a bowel movement prior to positioning on the scanner and the initial scan commencing.

For women of child-bearing potential, the urine β -hCG test for pregnancy will be performed. These subjects cannot participate in the study until the result of the urine β -hCG test is found to be negative.

At approximately 1 hour before injection of IMP, 12-lead ECG, and vital signs and oxygen saturation will be recorded, and a tolerability questionnaire filled out. Collection of urine will begin. A blood sample for biodistribution and radiation dosimetry will be collected. Two cannulas (or indwelling catheters) will be placed, one is in left/right arm/antecubital vein for blood sampling, the other is in contralateral side for IMP administration. The injection site will be examined for any abnormal findings prior to IMP administration.

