10.1.6 Tolerability Questionnaire Interview

Each subject is required to complete a tolerability questionnaire (see Appendix 15.4) at approximately 1 hour before injection and at approximately 15 minutes and 1, 4, 24, 48 hours after injection. The questionnaire evaluates subject mood, pain at injection site, itchiness of injection site, loss of function at injection site and quality of sleep using 100 mm visual analogue scales (VAS)* anchored by the following descriptors:

| | | |
|------------------------------------|--------------|--------------------------|
| Mood | Bad – 0mm | Good – 100mm |
| Pain at Injection Site | Normal – 0mm | Painful – 100mm |
| Itchiness of Injection Site | Normal – 0mm | Itchy – 100mm |
| Loss of Function at Injection Site | Normal – 0mm | Loss of Function – 100mm |
| Quality of Sleep | Bad – 0mm | Good – 100mm |

*Visual Analog Scale (VAS) is a continuous scale comprised of a horizontal line, usually 10 centimetres (100 mm) in length, anchored by 2 verbal descriptors: “0” stands for normal, and 100 mm stands for each symptom extreme, or “0” stands for bad, and 100 mm stands for good.

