12.5.6 Tolerability Questionnaire

The results of the tolerability questionnaire performed pre- and post-injection will be summarised. The boxplot of values over time will be plotted for each tolerability parameter.

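### The sleep item has no like-for-like pre-dose value, and the −1 h injection-site items may be scored before or after cannulation

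*Combined protocol and SAP*

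**What the plan says.** Section 10.1.6 states: "Each subject is required to complete a tolerability questionnaire (see Appendix 15.4) at approximately 1 hour before injection", and again at 15 minutes and 1, 4, 24 and 48 hours after it. There are five 100 mm VAS items: mood; pain, itchiness and loss of function at the injection site; and quality of sleep. Section 10.1 lists the questionnaire among the primary (safety) outcome measures.

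The footnote to Appendix 15.4 sets the reference period for sleep at each time:

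- −1 h: "assessment is based on how subject feels during past 2 weeks' sleep quality"
- 15 min, 1 h and 4 h: "assessments seem to be not applicable"
- 24 h: "assessment is based on quality of first sleep after IMP injection"
- 48 h: "assessment is based on quality of second sleep after IMP injection"

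Section 9.2.1 describes the −1 h procedures in one paragraph. ECG, vital signs and oxygen saturation come first, with "a tolerability questionnaire filled out. Collection of urine will begin" following. The dosimetry blood sample is next, then "Two cannulas (or indwelling catheters) will be placed", and last an inspection of the injection site before dosing.

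For analysis, section 12.5.6 calls for a summary of the questionnaire results before and after injection, and adds: "The boxplot of values over time will be plotted for each tolerability parameter".

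**The concern.** The study has one arm and no comparator, so a subject's own pre-dose score is the only reference within the study for the post-dose scores. Section 6.2.2 defends the safety plan partly because baseline and post-injection values can be compared within a subject. That needs the same question, asked under known conditions, on both sides of the injection.

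For sleep the question changes. A rating of the usual sleep over two weeks and a rating of one particular sleep are different quantities, and they will appear on one axis in the boxplot.

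For the three injection-site items the wording is constant, but the condition at −1 h is not fixed. Section 6.4 separates the risk of the IV procedure from that of the product, and section 8.1.1 gives reducing pain on injection as the reason for injecting slowly, so local discomfort is something the protocol cares about. If the −1 h score is taken before the cannula is in place, a later rise could come from the cannulation, from the product, or from both.

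**Working it through.** No formula applies. The documents give no effect size, standard deviation or target difference for the questionnaire, and section 12.8 reports no sample size calculation. The check sets the measurement rules beside the planned analysis.

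**Step 1: what is measured at each time (10.1.6, 15.4, 9.2.1).** Five items at six times give 5 × 6 = 30 cells per subject.

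| Item | −1 h | 15 min, 1 h, 4 h | 24 h, 48 h |
|---|---|---|---|
| Mood | same question | same question | same question |
| Injection-site pain, itch, loss of function | same question; cannula present or not is unstated | same question, after cannulation | same question, after cannulation |
| Sleep | 2-week recall | described as not applicable | one sleep each |

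**Step 2: sleep.** Three of the six cells apply: one with a 2-week recall and two with single-sleep recalls. There are two possible pre/post pairs, −1 h with 24 h and −1 h with 48 h, and neither uses the same recall period. Over the 8 planned subjects that is 2 × 8 = 16 pre/post comparisons, of which 0 are like for like. The 24 h and 48 h scores can be compared with each other, but both follow dosing.

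**Step 3: injection-site items.** There are 3 × 1 = 3 pre-dose cells and 3 × 5 = 15 post-dose cells per subject. The −1 h window in 15.4 is ±10 minutes, i.e. from 60 + 10 = 70 to 60 − 10 = 50 minutes before dosing. Section 9.2.1 puts the questionnaire and cannulation at about that same time, so the window does not settle which comes first. Two readings comply with the text:

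- Questionnaire first: the 3 pre-dose cells carry no cannula effect, while the 15 post-dose cells follow a cannulation.
- Cannulas first: the pre-dose cells already include cannulation.

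Nothing prevents the order from differing between subjects.

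**Step 4: mood.** All six cells use the same question and anchors. No mismatch is found.

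**Step 5: how the values are used.** Section 12.5 and the synopsis list the measures to be summarised as changes from baseline, and the questionnaire is not among them. It receives descriptive summaries and the boxplot. The general rule in section 12.1, under which the last pre-dose observation is baseline, would make −1 h the reference only if changes were calculated.

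**Result.** One item of five is shown to be non-comparable (sleep), three depend on an unstated order, and one is unaffected (mood).

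**The case against.** The strongest reply concerns the injection-site items. Section 9.2.1 groups everything under one approximate time and prescribes no sequence. It also mentions the blood sample before the cannula intended for blood sampling, so sentence order is weak evidence of chronology. This stands. A reader might infer that these items are always scored before cannulation and must sit near 0 mm at −1 h, making four of five items non-comparable. The documents do not support that; they show only that the order is open.

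A reader might also infer that every post-dose score includes a cannula in place. No section says how long the injection cannula stays in, and the sampling cannula is in the other arm. That reading is not established for the 24 h and 48 h scores in particular.

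Other measures bear on local tolerability. The injection site is inspected before dosing and at 4 h, abnormal findings are recorded as AEs (10.1.5), every AE receives a causality assessment (10.1.7), and site findings are summarised (12.5.7). These soften the consequence, but they do not replace the VAS scores as a reported outcome.

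The analysis is descriptive, with no confirmatory testing and no planned change from baseline, and the synopsis mentions only the post-dose questionnaires. That limits the harm. It does not remove it, because section 12.5.6 explicitly includes the pre-injection results and plots values over time, which invites the comparison.

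On sleep at 15 min, 1 h and 4 h, the appendix already signals that no score is expected, and missing values stay missing (12.6.5, 12.10). A blank would add nothing to the plot. This part is tidying only.

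Finally, a 2-week rating is a defensible measure of usual sleep. That is a reason to keep it, but not to plot it as the counterpart of single nights.

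**Conclusion.** The point holds in two parts of unequal strength. The sleep mismatch follows directly from Appendix 15.4: none of the pre/post pairs shares a recall period, so a pre/post difference in the planned summary and boxplot cannot be attributed to the product. The injection-site part is an ambiguity: section 9.2.1 leaves the order of questionnaire and cannulation open, so the three items lack a defined pre-dose condition.

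It would go too far to say that shifts in these scores reflect setting and cannulation. They could reflect setting, cannulation or the product, and a single-arm study cannot fully separate these. An overnight stay is implied by the 48-hour imaging visit but not stated, and the documents do not say where subjects sleep before dosing. They also give no VAS figure for cannula discomfort, so no size in millimetres can be assigned.

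The consequence is confined to the descriptive reading of a listed primary safety measure in 8 subjects. The change is worthwhile because it is cheap, not because the safety conclusion depends on it.

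**What to change.** 1. In Appendix 15.4, add at −1 h a rating of sleep for the night before dosing. Use it as the pre-dose value in the section 12.5.6 summary and boxplot, and report the 2-week rating separately as a descriptive item.
2. In sections 9.2.1 and 10.1.6, state that the −1 h injection-site items are completed after cannula placement and before the product is given, and that they refer to the planned injection arm.
3. As tidying, replace the loose wording on the early post-dose times with a statement that sleep is scored only at −1 h, 24 h and 48 h, and omit the other times from the sleep plot.

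The cost is one extra VAS line at −1 h and edits to wording and sequence, with no new visit or procedure. One night is a noisier baseline than a 2-week rating, which is why the latter should be kept. A previous-night rating may still differ from the post-dose nights in setting, so it aligns the recall period without removing every other explanation.
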